5.2.3.4 Prohibited Therapy

Subjects must be able to safely discontinue any prohibited medications or supplements listed in [Table 1](#) at least 2 weeks or 10 half-lives (whichever is longer) prior to the first dose of any study drug and not use these during the entire Treatment Period and for 30 days following discontinuation of study drugs.

Table 1. Prohibited Medications and Supplements

Medication or Supplement Name
Red yeast rice (monacolin K), St. John's Wort
Carbamazepine, phenytoin, pentobarbital, phenobarbital, primidone, rifabutin, rifampin
Atorvastatin, lovastatin, simvastatin*
Astemizole, cisapride, terfenadine
Efavirenz containing regimens

* Some HMG-CoA reductase inhibitors (including atorvastatin, lovastatin, or simvastatin) should not be taken with the study drugs. Subjects receiving these statins should either switch to pravastatin or rosuvastatin prior to the first dose of study drugs or may interrupt statin therapy throughout the treatment period and until 30 days after the last dose of study drug, based on the investigator's judgment. If switching to or continuing pravastatin or rosuvastatin, it is recommended to reduce the pravastatin dose by 50% or limit the rosuvastatin dose to 10 mg QD when taking with the study drugs.

Use of ethinyl estradiol containing oral contraceptives with ABT-493 and ABT-530 combination was associated with ALT increases in some healthy female subjects. Hormonal contraceptives (including oral, topical [including vaginal rings], injectable, or implantable varieties) containing ethinyl estradiol may not be used from 2 weeks prior to the first dose of ABT-493/ABT-530 until 30 days after the end of ABT-493/ABT-530 dosing. Progestin-only contraceptives, such as those containing norethindrone, desogestrel, or levonorgestrel, without ethinyl estradiol, may be used with ABT-493/ABT-530. Post-menopausal hormone replacement therapy, such as with esterified or conjugated estrogens, i.e., not containing ethinyl estradiol, may be used with ABT-493/ABT-530 at the discretion of the Investigator.

Anti-HCV medications other than those specified in the protocol will not be allowed anytime during the Treatment Period.

The chronic use of systemic immuno-suppressants is prohibited from 2 weeks prior to the first dose of study drug and until 30 days after the last dose of study drug including, but not limited to, corticosteroids (prednisone equivalent of > 10 mg/day for > 2 weeks), azathioprine, or monoclonal antibodies (e.g., infliximab).

For HCV/HIV-1 Co-Infected Subjects

The investigator must refer to the current package insert(s) or product label(s) of the subject's ART regimen for a complete list of prohibited medications.

5.2.4 Contraception Recommendations

If female, subject must be either:

- Postmenopausal defined as:
 - Age \geq 55 years with no menses for 12 or more months without an alternative medical cause.
 - Age $<$ 55 years with no menses for 12 or more months without an alternative medical cause AND an FSH level $>$ 40 IU/L.OR
- Permanently surgically sterile (bilateral oophorectomy, bilateral salpingectomy or hysterectomy).
OR
- Women of Childbearing Potential (WOCBP):
 - Practicing at least one of the following methods of birth control, on Study Day 1 (or earlier) through at least 30 days after the last dose of study drug.
 - Progestogen-only hormonal contraception (oral, injectable, implantable) associated with inhibition of ovulation, initiated at least 1 month prior to Study Day 1.
 - Bilateral tubal occlusion/ligation.
 - Vasectomized partner(s), provided the vasectomized partner has received medical assessment of the surgical success and is the sole sexual partner of the WOCBP trial participant.
 - Intrauterine device (IUD).
 - Intrauterine hormone-releasing system (IUS), excluding ethinyl estadiol.
 - Male or female condom with or without spermicide.
 - Cap, diaphragm or sponge with spermicide.

- A combination of male condom with either cap, diaphragm or sponge with spermicide (double barrier method).
- True abstinence: Refraining from heterosexual intercourse when this is in line with the preferred and usual lifestyle of the subject (periodic abstinence [e.g., calendar, ovulation, symptothermal, post-ovulation methods] and withdrawal are not acceptable).

If required per local practices, male or female condom with or without spermicide OR cap, diaphragm or sponge with spermicide should be used in addition to one of the birth control methods listed above (excluding true abstinence).

If the male subject has a female partner who is postmenopausal or permanently sterile (bilateral oophorectomy, bilateral salpingectomy or hysterectomy), no contraception is required.

If the male subject is sexually active with female partner(s) of childbearing potential, he must agree from Study Day 1 through 90 days after the last dose of study drug to practice contraception with:

- Condom use and female partner(s) using at least one of the contraceptive measures (as defined in the protocol for female study subjects of childbearing potential).
- True abstinence: Refraining from heterosexual intercourse – when this is in line with the preferred and usual lifestyle of the subject. (Note: Periodic abstinence [e.g., calendar, ovulation, symptothermal, post-ovulation methods] and withdrawal are not acceptable).
- Additionally, male subject agrees not to donate sperm from Study Day 1 through 90 days after the last dose of study drug.

5.3 Efficacy Pharmacokinetic, Pharmacogenetic and Safety Assessments/Variables

5.3.1 Efficacy and Safety Measurements Assessed and Flow Chart

Study procedures are described in the following section of this protocol and are summarized in tabular format in [Appendix C](#).

5.3.1.1 Study Procedures

Informed Consent Information

Signed study-specific informed consent will be obtained from the subject before any study procedures are performed. Details about how informed consent will be obtained and documented are provided in Section [9.3](#).

Medical History

A complete medical history, including history of alcohol, tobacco and nicotine-containing product use, will be taken at Screening. The medical history will be updated on Study Day 1. The medical history obtained prior to the first dose of study drug will serve as the baseline for clinical assessment.

Physical Examination

Physical examinations will be performed at visits specified in [Appendix C](#) or upon subject discontinuation. A symptom-directed physical examination will be performed when necessary. The physical examination performed on Study Day 1 will serve as the baseline physical examination for clinical assessment. Any significant physical examination findings after dosing will be recorded as adverse events.

Height will be measured only at Screening. Waist circumference will be measured at the Screening Visit, but if it is not measured at Screening, it may be measured on Study Day 1.

Vital Signs and Weight

Body temperature, blood pressure, pulse and weight will be measured at each study visit as specified in [Appendix C](#) or upon subject discontinuation. The subject will wear lightweight clothing and no shoes during weighing. Blood pressure and pulse rate will be measured after the subject has been sitting for at least 3 minutes. The vital signs measurements on Study Day 1 will serve as the baseline measurements for clinical assessment.

12-Lead Electrocardiogram (ECG)

A single 12-lead resting ECG will be obtained at the visits indicated in [Appendix C](#) or upon subject discontinuation. The ECG obtained at Screening will serve as the baseline measurement for clinical assessment. The ECG should be performed prior to blood collection.

Each ECG will be evaluated by an appropriately qualified physician at the site ("local reader"), preferably a cardiologist. This reading of the ECG will be used by the investigator for subject safety assessments, including adverse event determination and management, and decision on whether a subject will be discontinued from the study.

The local reader will sign and date all the ECGs collected in this study and provide a global interpretation for each ECG using the following categories:

- Normal ECG
- Abnormal ECG – Not clinically significant (NCS)
- Abnormal ECG – Clinically significant (CS)

All local reader's evaluations of ECGs will be entered into the electronic source documents, electronic case report forms or paper case report forms. All ECG source documentation will be retained at the study site. The automatic cardiograph reading (i.e., cardiograph-generated measurements and interpretations) will not be collected for analysis.

Clinical Laboratory Tests

Samples will be obtained at a minimum for the clinical laboratory tests listed in [Table 2](#) at the visits indicated in [Appendix C](#).

The blood samples for serum chemistry tests should be collected following a minimum 8-hour fast prior to study drug intake (with the exception of the Screening Visit, which may be non-fasting). Subjects whose visits occur prior to the morning dose of study drug should be instructed to fast after midnight until the blood sample is collected in the morning and thereafter take their study medications with food. Subjects whose visits occur following the morning dose of study drug should be instructed to fast after breakfast until the study visit occurs. At the Study Day 1 visit, a fasting blood sample should be collected prior to the first dose of study drug. Blood samples should still be drawn if the subject did not fast for at least 8 hours. Fasting or non-fasting status will be recorded in the source documents and on the laboratory requisition. The baseline laboratory test results for clinical assessment for a particular test will be defined as the last measurement prior to the initial dose of study drug.

A central laboratory will be utilized to process and provide results for the clinical laboratory tests.

Instructions regarding the collection, processing, and shipping of these samples will be found in the laboratory manual provided by the central laboratory chosen for this study. The certified laboratory chosen for this study is Covance.

Table 2. Clinical Laboratory Tests

Hematology	Clinical Chemistry	Other Tests
Hematocrit	Blood Urea Nitrogen (BUN)	HBsAg ^c
Hemoglobin	Creatinine	HBV DNA (if HBsAg is negative) ^c
Red Blood Cell (RBC) count	Total bilirubin	HCV Ab ^c
White Blood Cell (WBC) count	Direct and indirect bilirubin	HIV Ab ^c
Neutrophils	Alanine aminotransferase (SGPT/ALT)	Opiates ^c
Bands, if detected	Aspartate aminotransferase (SGOT/AST)	Barbiturates ^c
Lymphocytes	Alkaline phosphatase	Amphetamines ^c
Monocytes	Sodium	Cocaine ^c
Basophils	Potassium	Benzodiazepines ^c
Eosinophils	Calcium	Alcohol ^c
Platelet count (estimate not acceptable)	Inorganic phosphorus	Phencyclidine ^c
Reticulocyte count	Uric Acid	Propoxyphene ^c
Prothrombin Time/INR	Cholesterol	Methadone ^c
Activated partial thromboplastin time (aPTT)	Total protein	Hemoglobin A1C ^c
	Glucose	HCV genotype and subtype ^c
Urinalysis	Triglycerides	Urine and Serum:
Specific gravity	Low Density Lipoproteins (LDL) ^{a,b}	Human Chorionic Gonadotropin (hCG) for females ^f
Ketones	High Density Lipoprotein (HDL) ^b	Hepatitis B Panel ^g
pH	Albumin	HCV RNA
Protein	Chloride	Plasma HIV-1 RNA ^h
Blood	Bicarbonate	HIV-1 genotypic resistance testing (if applicable) ^h
Glucose	Magnesium	IL28B
Urobilinogen	Total insulin	CD4, ^h CD4% ^h
Bilirubin	Gamma-glutamyl transferase (GGT)	CD8, ^h CD8% ^h
Leukocyte esterase	Creatine phosphokinase (CPK)	CD4: CD8 ^h
Microscopic (reflex)	Follicle stimulating hormone (FSH) ^c	Alpha fetoprotein
	Creatinine clearance (Cockcroft Gault calculation)	Alpha2-macroglobulin ⁱ
	eGFR (C-MDRD) ^d	Haptoglobin ⁱ
		Apolipoprotein A1 ⁱ

a. Directly Measured.

b. Performed only at Baseline.

c. FSH at Screening only for female subjects to assess postmenopausal state.

d. eGFR calculated by the MDRD formula, modified for the Chinese population (C-MDRD).

e. Performed only at Screening.

f. Pregnancy testing is not required for females of non-childbearing potential.

Table 2. Clinical Laboratory Tests (Continued)

- g. Performed for management of transaminase elevations (Section 6.1.7.1).
- h. Only for HCV/HIV co-infected subjects.
- i. Component of FibroTest collected only if needed during the Screening Period.

For any laboratory test value outside the reference range that the investigator considers clinically significant:

- The investigator will repeat the test to verify the out-of-range value.
- The investigator will follow the out-of-range value to a satisfactory clinical resolution.
- A laboratory test value that requires a subject to be discontinued from the study or study drug or requires a subject to receive treatment will be recorded as an adverse event.

The management of laboratory abnormalities that may occur during the study is described in Section 6.1.7.

Pregnancy Test

A serum pregnancy test will be performed for all female subjects of childbearing potential at Screening. Subjects with borderline pregnancy tests at Screening must have a serum pregnancy test ≥ 3 days later to document continued lack of a positive result. Additional urine pregnancy tests will be performed at all the visits indicated in [Appendix C](#).

Pregnancy testing is not required for females of non-childbearing potential.

Determination of postmenopausal status will be made during the Screening period, based on the subject's history.

Concomitant Medication Assessment

Use of medications (prescription or over-the-counter, including vitamins, herbal supplements, and vaccines) from the time of signing the consent, through the Treatment Period and 30 days after study drugs are stopped must be recorded in the eCRF at each study visit indicated in [Appendix C](#) (Treatment Period). Thereafter, only medications

taken for SAEs and treatment of HCV and HIV will be recorded in the eCRF at each study visit indicated in [Appendix C](#) (Post-Treatment Period).

Hepatitis and HIV Screen

HBsAg (hepatitis B surface antigen), HBV DNA (if HBsAg is negative), HCV Ab and HIV Ab tests will be performed at Screening. The tests will be performed by a certified laboratory. The investigator must discuss any local reporting requirements to local health agencies with the subject. The site will report these results per local regulations, if necessary.

Urine Screens for Drugs of Abuse

A urine screen for drugs of abuse will be performed at Screening. The panel for drugs of abuse will minimally include drugs listed in [Table 2](#). Any positive result must be assessed for clinical significance.

These analyses will be performed by the certified central laboratory chosen for the study.

Liver Diagnostic Testing

Subjects who have not had a qualifying liver biopsy within the previous 24 months or who have not had a qualifying FibroScan[®] within the previous 6 months but otherwise meet all of the inclusion criteria and none of the exclusion criteria will undergo liver biopsy or non-invasive testing (FibroTest and APRI or FibroScan[®]) for assessment of cirrhosis prior to enrollment. Selection of liver biopsy or non-invasive testing performed should be based on local standard practice.

Biopsy results as per METAVIR, Batts-Ludwig, Knodell, IASL, Scheuer, or Laennec gradings with fibrosis score of > 3 (including 3 – 4 or 3/4), or Ishak grading with fibrosis score of > 4 are acceptable for ascertaining presence of compensated cirrhosis. Subjects with historical liver FibroScan[®] or biopsy results are acceptable if these were conducted within 6 or 24 months from Screening, respectively, and the results are not exclusionary. In a subject with an indeterminate FibroTest result ($0.48 < \text{result} < 0.75$), or conflicting

FibroTest and APRI results (e.g., FibroTest ≥ 0.75 , but APRI ≤ 2) at Screening, liver FibroScan[®] or biopsy can be performed during Screening to ascertain the presence or absence of cirrhosis. Subjects with indeterminate FibroScan[®] score ($12.5 \leq \text{score} < 14.6$) may only be enrolled if they have a qualifying liver biopsy performed within 24 months prior to or during Screening.

Child-Pugh Score and Category

The Child-Pugh score uses five clinical measures of liver disease (3 laboratory parameters and 2 clinical assessments; [Table 3](#)). Child-Pugh score will be determined at the visits indicated in [Appendix C](#).

Table 3. Child-Pugh Classification of Severity of Cirrhosis

Parameter	Points Assigned for Observed Findings		
	1	2	3
Total bilirubin, $\mu\text{mol/L}$ (mg/dL)	< 34.2 (< 2)	34.2 – 51.3 (2 – 3)	> 51.3 (> 3)
Serum albumin, g/L (g/dL)	> 35 (> 3.5)	28 – 35 (2.8 – 3.5)	< 28 (< 2.8)
INR	< 1.7	1.7 – 2.3	> 2.3
Ascites*	None	Slight	Moderate to severe
Hepatic encephalopathy**	None	Grade 1 or 2 (or suppressed with medication)	Grade 3 or 4 (or refractory)

* None; Slight ascites = Ascites detectable only by ultrasound examination; Moderate ascites = Ascites manifested by moderate symmetrical distension of the abdomen; Severe ascites = Large or gross ascites with marked abdominal distension.

** Grade 0: normal consciousness, personality, neurological examination, electroencephalogram; Grade 1: restless, sleep disturbed, irritable/agitated, tremor, impaired handwriting, 5 cps waves; Grade 2: lethargic, time-disoriented, inappropriate behavior, asterixis, ataxia, slow triphasic waves; Grade 3: somnolent, stuporous, place-disoriented, hyperactive reflexes, rigidity, slower waves; Grade 4: unarousable coma, no personality/behavior, decerebrate, slow 2 to 3 cps delta activity.

Clinical Assessment of Hepatic Decompensation

A clinical assessment of hepatic encephalopathy and ascites will be performed at Study Day 1 prior to dosing to confirm the subject has not progressed to hepatic decompensation since Screening.

Hepatocellular Carcinoma Screening: Liver Ultrasound and Alpha Fetoprotein

In order to monitor for the presence of hepatocellular carcinoma (HCC), alpha fetoprotein will be assayed and an ultrasound of the liver will be performed as indicated in [Appendix C](#). A positive Ultrasound result suspicious for HCC at screening will be confirmed with CT scan or MRI during the screening period. Suspicious ultrasound lesions confirmed by CT or MRI are exclusionary.

Patient Reported Outcomes (PRO) Instruments (Questionnaires)

Subjects will complete the self-administered PRO instruments (where allowed per local regulatory guidelines) on the study days specified in [Appendix C](#). Subjects should be instructed to follow the instructions provided with each instrument and to provide the best possible response to each item. Site personnel shall not provide interpretation or assistance to subjects other than encouragement to complete the tasks. Subjects who are functionally unable to read any of the instruments may have site personnel read the questionnaires to them. Site personnel should encourage completion of each instrument at all specified visits and should ensure that a response is entered for all items.

EuroQol-5 Dimensions-3 Level (EQ-5D-3L)

The EQ-5D-3L is a health state utility instrument that evaluates preference for health status (utility). The 5 items in the EQ-5D-3L comprise 5 dimensions (mobility, self-care, usual activities, pain/discomfort, and anxiety/depression) each of which are rated on 3 levels of severity. Responses to the 5 items encode a discrete health state which is mapped to a preference (utility) specific for different societies. Subjects also rate their perception of their overall health on a separate visual analogue scale (VAS). The EQ-5D-3L should require approximately 5 minutes to complete.

Fatigue Severity Scale (FSS)

The FSS measures the impact of fatigue over the past week on specific types of functioning (e.g., motivation, exercise, physical functioning, carrying out duties, interfering with work, family, or social life). The survey consists of 9 questions using

a 7-point Likert scale. A total score is calculated as the average of the individual item responses. The scale's psychometric properties have been confirmed in chronic hepatitis C and other diseases. The FSS should require approximately 5 minutes to complete.

PRO instruments should be completed prior to drug administration on Study Day 1 and prior to any discussion of adverse events or any review of laboratory findings, including HCV RNA levels.

Enrollment and Assignment of Subject Numbers

All screening activities must be completed and reviewed prior to enrollment. Subjects who meet all the Inclusion Criteria and none of the Exclusion Criteria at Screening will proceed to enrollment via the IRT system on Study Day 1.

Screening numbers will be unique 6-digit numbers and will begin with 100201 with the first three digits representing the investigative site, and the last three digits representing the subject at that site. Enrolled subjects will keep their screening number as their subject number throughout the study.

Study Drug Compliance for Kits

Individual kits of ABT-493/ABT-530 will be provided for subject dosing to the site. Each subject will have compliance documented by the site in the subject's source notes for ABT-493/ABT-530. At each Study Drug Accountability Visit in [Appendix C](#), the overall number of tablets of ABT-493/ABT-530 remaining in each kit will be recorded in the source and entered in the IRT system along with the date of reconciliation.

HCV Genotype and Sub-Genotype

Plasma samples for HCV genotype and sub-genotype determination will be collected at Screening. Genotype and sub-genotype will be assessed using the appropriate assay by the central laboratory.

HCV RNA Levels

Plasma samples for HCV RNA levels will be collected as indicated in [Appendix C](#). Plasma HCV RNA levels will be determined by an approved HCV RNA quantitative assay for each sample collected by the central laboratory including but not limited to Roche COBAS[®] AmpliPrep/COBAS[®] TaqMan[®] HCV Quantitative Test, v 2.0.

HCV Resistance Testing Sample

A plasma sample for HCV resistance testing will be collected prior to dosing on Study Day 1 and at the study visits indicated in [Appendix C](#). Specific instructions for preparation and storage of HCV RNA and HCV resistance samples will be provided by the central laboratory, AbbVie, or its designee.

Flow Cytometry, HIV-1 RNA and HIV Resistance Testing Samples

Samples for plasma HIV-1 RNA levels and flow cytometry (including but not limited to CD4+ T-cell and CD8+ T-cell counts [absolute and percent]) will be obtained at the times specified in [Appendix C](#).

If a subject who is on stable HIV-1 ART has an HIV-1 RNA level ≥ 200 copies/mL, the subject's HIV-1 RNA is to be repeated as noted in Section 5.4.1.2. At the time the repeat plasma HIV-1 RNA is drawn, a sample may be obtained for HIV-1 genotypic resistance testing. If the subject's repeat HIV-1 RNA is ≥ 500 copies/mL, the sample obtained for HIV-1 genotypic resistance testing may be analyzed as indicated by local standard of care.

If the subject's repeat HIV-1 RNA is < 200 copies/mL, then the subject will resume routine plasma HIV-1 RNA assessments as shown in [Appendix C](#) and described in Section 5.4.1.2.

Specific instructions for preparation and storage of flow cytometry, plasma HIV-1 RNA, and HIV resistance samples, if applicable, will be provided by the central laboratory, AbbVie, or its designee.

Archive Plasma Sample

Archive plasma samples will be collected at the study visits, indicated in [Appendix C](#). Archive plasma samples are being collected for possible additional analyses, including but not limited to, study drug or metabolite measurements, viral load, safety/efficacy assessments, HCV gene sequencing, HCV resistance testing, and other possible predictors of response, as determined by AbbVie.

Specific instructions for preparation and storage of archive samples will be provided by the central laboratory, AbbVie, or its designee.

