5.5 Treatments

5.5.1 Treatments Administered

Each dose of study drug (ABT-493/ABT-530) will be dispensed in the form of film-coated co-formulated tablets at the visits listed in [Appendix C](#). Subjects will be instructed to take study drugs at the same time every day with food. Prior to all visits with pharmacokinetic sampling, the date and time of the two previous doses will be recorded to the nearest minute in the source documents and the eCRF. For subjects participating in Intensive PK sampling on Study Day 1 and at the Week 4 visit, they will have their dose administered by study site personnel after food and blood samples are collected for assay of study drugs. The date and time of dosing and blood sample collection will be recorded to the nearest minute in the source document.

ABT-493/ABT-530 will be provided by AbbVie as 100 mg/40 mg film-coated tablets. ABT-493/ABT-530 will be taken orally as ABT-493 300 mg/ABT-530 120 mg (three × ABT-493 100 mg/ABT-530 40 mg tablets) QD and with food.

Study drug must not be dispensed without contacting the IRT system. Study drug may only be dispensed to subjects enrolled in the study through the IRT system. At the end of the Treatment Period or at the Premature D/C Visit from the Treatment Period, the site will contact the IRT system to provide visit date information and study drug return information for each kit (Section [5.5.7](#)).

All subjects who receive at least one dose of study drug and meet the HCV virologic stopping criteria or fail to maintain HIV virologic suppression should follow instructions in Section [5.4.1.1](#) and Section [5.4.1.2](#), respectively.

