- Baseline alpha fetoprotein (< 20 or ≥ 20 ng/mL);
- Baseline Child-Pugh score (5, 6, or > 6);
- Baseline fibrosis stage (equivalent to Metavir F0 – F1, F2, F3, F4 [if applicable]);
- History of diabetes (yes/no);
- History of bleeding disorders (yes/no);
- History of depression or bipolar disorder (yes/no);
- History of cardiovascular disease (yes/no);
- Baseline metabolic syndrome (yes/no);
- Injection drug use (yes, within last 12 months; yes, more than 12 months ago; or no);
- Baseline stable opiate substitution use (yes/no);
- Baseline hepato-protectant medication use (as determined by investigator on concomitant medication eCRF, yes/no);
- Tobacco use (user, ex-user, or non-user);
- Alcohol use (drinker, ex-drinker, or non-drinker);
- Baseline total bilirubin (< 34.2 or ≥ 34.2 umol/L);
- Baseline total INR (< 1.7 or ≥ 1.7);
- Baseline creatinine clearance (Cockcroft-Gault) (< 60, ≥ 60 to < 90, or ≥ 90 mL/min);
- Baseline eGFR (C-MDRD) (< 60, ≥ 60 to < 90, or ≥ 90 mL/min/1.73 m^2);
- Concomitant use of Proton Pump Inhibitors (PPIs) (yes/no).

The demographic and baseline characteristics specified above, along with the following, will be summarized for subjects with HCV/HIV co-infection at Screening for the overall safety population and for the geographic region of China:

- HIV-1 treatment status (antiretroviral therapy [ART]-Naïve, ART-Treated);
- HIV-1 ART regimen (e.g., raltegravir [RAL], dolutegravir [DTG], rilpivirine [RPV]) for those receiving ART (as determined by investigator on concomitant medication eCRF) at baseline;
- Baseline CD4+ T-cell count (continuous; and < 200, 200 to < 350, 350 to < 500, or  $\geq 500$  cells/mm^3).

Any concomitant medication coded to the WHO Drug Dictionary ATC code of A02BC will be counted as a PPI.

If the IL28B genotype result is not available from a sample collected during the Screening period, then a result available from a sample collected at any time during the study will be used to summarize IL28B genotype.

HOMA-IR is defined as  $\text{fasting glucose (mmol/L)} \times \text{fasting insulin } (\mu\text{IU/mL}) \div 22.5$ . Subjects who do not have concurrent fasting glucose and fasting insulin values at baseline will be excluded from the summary of baseline HOMA-IR.

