#### **11.3 Analysis of Laboratory Data**

Data collected from the central and local laboratories, including additional laboratory testing due to a serious AE, will be used in all analyses.

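### The SAP pools fasting and non-fasting chemistry samples, so high-side glucose and triglyceride summaries, and insulin change and shift, may be biased upward with no control arm to reveal it

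*Protocol*

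**What the plan says.** **Collection (protocol 5.3.1.1, Clinical Laboratory Tests).** The general rule, with Screening exempt, is: "The blood samples for serum chemistry tests should be collected following a minimum 8-hour fast prior to study drug intake". Subjects seen before the morning dose fast from midnight. For the others, "Subjects whose visits occur following the morning dose of study drug should be instructed to fast after breakfast until the study visit occurs", with no minimum number of hours. For baseline, "At the Study Day 1 visit, a fasting blood sample should be collected prior to the first dose of study drug". A short fast does not cancel a sample: "Blood samples should still be drawn if the subject did not fast for at least 8 hours". The status is captured: "Fasting or non-fasting status will be recorded in the source documents and on the laboratory requisition".

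**Dosing (protocol 5.5.1).** "Subjects will be instructed to take study drugs at the same time every day with food".

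**Analysis (SAP 11.3 to 11.3.2).** Central and local laboratory data, "including additional laboratory testing due to a serious AE, will be used in all analyses". Baseline is the latest available pre-dose value, whatever its fasting status. Each parameter gets mean change by visit. Chemistry values get shifts to the on-treatment minimum and maximum. Table 11 parameters get the maximum on-treatment grade, counted only if worse than the baseline grade. Table 11 grades high glucose (Grade 2 above 8.9 mmol/L) and triglycerides (Grade 1 above 1.71 mmol/L) without a fasting condition. Insulin has no row there.

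**Where the SAP does use fasting status (7.1).** "Subjects who do not have concurrent fasting glucose and fasting insulin values at baseline will be excluded from the summary of baseline HOMA-IR". Table 8 also names fasting glucose as a metabolic syndrome criterion.

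**The concern.** The two fasting instructions do not fit together. Someone who takes the dose with breakfast and attends later that morning follows the second sentence and misses the 8-hour rule. On Day 1 every procedure apart from the optional post-dose PK samples precedes the first dose (Appendix C, footnote a). A post-dose, post-breakfast chemistry sample can therefore occur only after baseline, and the asymmetry comes from the schedule itself.

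The analysis then compares later values with baseline as if the sampling state were the same. The maximum-grade rule adds to this, because one fed sample among five or six on-treatment visits can be enough to count a subject. Safety is a primary objective (protocol 4.1) and there is one arm (protocol 8.3), so no concurrent group would show the same meal-related rise. The tables as planned could not separate a meal artefact from a drug effect, although the information needed to do so is recorded.

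**Working it through.** **No plan figure to reproduce.** The documents give no expected non-fasting share, post-meal increment, glucose or triglyceride distribution, or expected grade rate. What follows is illustration over a range, not estimation.

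**1. Which summaries are exposed.**
- Glucose and triglycerides: mean change, shift to maximum and high-side Table 11 grades.
- Insulin: mean change and shift only. It is collected at Day 1 and end of treatment (SAP Table 1 note) and is not graded.
- Not exposed to this upward bias: low-glucose grades, shifts to minimum, SVR12.
- On-treatment visits: Weeks 1, 2, 4, 8 and 12 (five), plus Week 16 for 16-week subjects (six). The end-of-treatment visit is the Week 12 or Week 16 visit, not an additional one.

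**2. Mean change.** Let f be the non-fasting share and d the average post-meal increment:

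bias = (f_on-treatment − f_baseline) × d

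With all baselines fasting (f_baseline = 0):
- glucose, f from 10% to 50% and d from 0.5 to 2 mmol/L: 0.10 × 0.5 = +0.05 up to 0.50 × 2 = +1.0 mmol/L;
- triglycerides, the same f and d from 0.2 to 1.0 mmol/L: 0.10 × 0.2 = +0.02 up to 0.50 × 1.0 = +0.5 mmol/L.

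If the two shares are equal the bias is zero. If baseline has the larger share, the sign reverses.

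**3. Maximum grade, simulated with no drug effect.** There are 400,000 simulated subjects with five on-treatment visits, each independently non-fasting with probability f, and all baselines fasting. Every distribution input is an assumption:
- fasting glucose: mean 5.6, between-subject SD 0.9, within-subject SD 0.5 mmol/L; an event is a maximum above 8.9 with baseline at or below 8.9;
- triglycerides: median 1.1 mmol/L, log-scale SD 0.4 between and 0.2 within subjects; an event is any Table 11 grade worse than baseline.

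| Non-fasting share | New Grade 2+ glucose; d = 0.5 / 1 / 2 mmol/L | Any triglyceride worsening; post-meal ratio 1.1 / 1.25 / 1.5 |
|---|---|---|
| 0% | 0.2% | about 17.7% |
| 10% | 0.31 / 0.71 / 4.74% | 18.8 / 21.1 / 26.7% |
| 30% | 0.49 / 1.60 / 11.56% | 20.7 / 27.0 / 40.1% |
| 50% | 0.65 / 2.31 / 16.04% | 22.4 / 31.5 / 49.0% |

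In 160 subjects, the all-fasting glucose rate is 0.0021 × 160 ≈ 0.3 subjects. At 10% non-fasting it is 0.0031 × 160 ≈ 0.5 to 0.0474 × 160 ≈ 7.6. At 50% it is 0.0065 × 160 ≈ 1.0 to 0.1604 × 160 ≈ 25.7.

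**4. Reading the triglyceride column.** The 17.7% with every sample fasting comes from comparing a maximum over five visits with a single baseline. Only the excess over that figure is due to meals.

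**5. With fasting samples only at both time points,** the meal term in step 2 is zero by construction.

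**The case against.** The strongest reply is that the 8-hour rule governs every visit except Screening. Read under it, the after-breakfast sentence may describe a visit late enough in the day to satisfy both instructions. No section schedules a mid-morning, post-meal draw. This stands as far as it goes: post-meal sampling is an open route, not the plan. But the sentence sets no minimum hours, and short-fast samples are kept, so the route is not closed either.

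A reader might infer that baseline is always fasting and that the results are therefore biased upward. The documents do not support that. Short-fast Day 1 samples are also kept. If a Day 1 glucose or triglyceride value is missing, a Screening value, which may be non-fasting, becomes baseline. Both push the other way.

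A reader might also compute per-sample rates for fed samples. With an assumed fasting mean of 5.8 and SD of 1.2 mmol/L, exceedance of 8.9 rises from 0.5% to 4%, 18% or 47% for increments of 1, 2 or 3 mmol/L. That arithmetic is correct, but it treats every sample as fed and leaves out the non-fasting share.

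Finally, restricting the main grade table to fasted samples would drop genuinely high values from local or SAE-related draws, which SAP 11.3 deliberately includes. That is a fair objection to a fasted-only main analysis, and the fix below avoids it. It is also true that the likelier error overstates harm, and that these analytes are not among the adverse events of special interest or the hepatotoxicity criteria.

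**Conclusion.** The concern holds as a possible bias, not a demonstrated one. The protocol leaves a post-meal sampling route open after baseline, the SAP pools the values, and a single-arm trial has nothing to set the resulting rise against. The direction is upward whenever more on-treatment than baseline samples are non-fasting. The size runs from negligible (0.3% against 0.2% for new Grade 2+ glucose) to large (16%). The documents cannot narrow this range, which rests on assumed distributions, assumed meal increments, independent visits and fasting baselines.

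This is a safety-reporting weakness. The primary efficacy estimate and its interval do not depend on it. It is still worth correcting before analysis, because the SAP already relies on fasting status for baseline HOMA-IR and the status is recorded at collection.

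**What to change.** **SAP 11.3.2.** Keep the all-samples summaries and all listings as planned. Beside them, add summaries restricted to samples flagged as fasted at least 8 hours at both baseline and post-baseline:
- glucose and triglycerides: change from baseline, shift and high-side Table 11 grades;
- insulin: change from baseline and shift.

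Samples without a flag, such as local or SAE-related draws, count only in the all-samples version. Confirm that the fasting flag reaches the analysis dataset: the protocol places it in source documents and on the requisition, and does not say that it is transferred.

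**Protocol 5.3.1.1.** Reconcile the 8-hour sentence with the after-breakfast sentence so that sites have one consistent instruction.

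**Cost.** SAP wording, a few extra tables and one filter on a status already recorded. The fasting-only version will have fewer samples per visit. No safety value leaves the main tables.
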